Day 15 Post-Dose 1	XX	X.XX	X.XX, X.XX	XX	X.XX	X.XX, X.XX	XX	X.XX	X.XX, X.XX
Day 29 Post-Dose 1	XX	X.XX	X.XX, X.XX	XX	X.XX	X.XX, X.XX	XX	X.XX	X.XX, X.XX
Day 15 Post-Dose 2	XX	X.XX	X.XX, X.XX	XX	X.XX	X.XX, X.XX	XX	X.XX	X.XX, X.XX
Day 29 Post-Dose 2	XX	X.XX	X.XX, X.XX	XX	X.XX	X.XX, X.XX	XX	X.XX	X.XX, X.XX
Day 57 Post-Dose 2	XX	X.XX	X.XX, X.XX	XX	X.XX	X.XX, X.XX	XX	X.XX	X.XX, X.XX
Day 180 Post-Dose 2	XX	X.XX	X.XX, X.XX	XX	X.XX	X.XX, X.XX	XX	X.XX	X.XX, X.XX
LNI									
Day 1 (pre-vaccination)	XX	X.XX	X.XX, X.XX	XX	X.XX	X.XX, X.XX	XX	X.XX	X.XX, X.XX
Day 15 Post-Dose 1	XX	X.XX	X.XX, X.XX	XX	X.XX	X.XX, X.XX	XX	X.XX	X.XX, X.XX
Day 29 Post-Dose 1	XX	X.XX	X.XX, X.XX	XX	X.XX	X.XX, X.XX	XX	X.XX	X.XX, X.XX
Day 15 Post-Dose 2	XX	X.XX	X.XX, X.XX	XX	X.XX	X.XX, X.XX	XX	X.XX	X.XX, X.XX
Day 29 Post-Dose 2	XX	X.XX	X.XX, X.XX	XX	X.XX	X.XX, X.XX	XX	X.XX	X.XX, X.XX
Day 57 Post-Dose 2	XX	X.XX	X.XX, X.XX	XX	X.XX	X.XX, X.XX	XX	X.XX	X.XX, X.XX
Day 180 Post-Dose 2	XX	X.XX	X.XX, X.XX	XX	X.XX	X.XX, X.XX	XX	X.XX	X.XX, X.XX

Table 31: PRNT₅₀ Geometric Mean Titer (GMT) and Log Neutralizing Titer Index (LNI) Results with 95% Confidence Intervals by Study Day and Treatment Group, Per Protocol Population

Visit	HydroVax-002 YFV 1 meg			HydroVax-002 YFV 5 meg			Placebo		
	N	GMT	95% CI	N	GMT	95% CI	N	GMT	95% CI
PRNT₅₀									
Day 1 (pre-vaccination)	XX	X.XX	X.XX, X.XX	XX	X.XX	X.XX, X.XX	XX	X.XX	X.XX, X.XX
Day 15 Post-Dose 1	XX	X.XX	X.XX, X.XX	XX	X.XX	X.XX, X.XX	XX	X.XX	X.XX, X.XX
Day 29 Post-Dose 1	XX	X.XX	X.XX, X.XX	XX	X.XX	X.XX, X.XX	XX	X.XX	X.XX, X.XX
Day 15 Post-Dose 2	XX	X.XX	X.XX, X.XX	XX	X.XX	X.XX, X.XX	XX	X.XX	X.XX, X.XX
Day 29 Post-Dose 2	XX	X.XX	X.XX, X.XX	XX	X.XX	X.XX, X.XX	XX	X.XX	X.XX, X.XX
Day 57 Post-Dose 2	XX	X.XX	X.XX, X.XX	XX	X.XX	X.XX, X.XX	XX	X.XX	X.XX, X.XX
Day 180 Post-Dose 2	XX	X.XX	X.XX, X.XX	XX	X.XX	X.XX, X.XX	XX	X.XX	X.XX, X.XX
LNI									
Day 1 (pre-vaccination)	XX	X.XX	X.XX, X.XX	XX	X.XX	X.XX, X.XX	XX	X.XX	X.XX, X.XX
Day 15 Post-Dose 1	XX	X.XX	X.XX, X.XX	XX	X.XX	X.XX, X.XX	XX	X.XX	X.XX, X.XX
Day 29 Post-Dose 1	XX	X.XX	X.XX, X.XX	XX	X.XX	X.XX, X.XX	XX	X.XX	X.XX, X.XX
Day 15 Post-Dose 2	XX	X.XX	X.XX, X.XX	XX	X.XX	X.XX, X.XX	XX	X.XX	X.XX, X.XX
Day 29 Post-Dose 2	XX	X.XX	X.XX, X.XX	XX	X.XX	X.XX, X.XX	XX	X.XX	X.XX, X.XX
Day 57 Post-Dose 2	XX	X.XX	X.XX, X.XX	XX	X.XX	X.XX, X.XX	XX	X.XX	X.XX, X.XX
Day 180 Post-Dose 2	XX	X.XX	X.XX, X.XX	XX	X.XX	X.XX, X.XX	XX	X.XX	X.XX, X.XX

Table 32: Number of Subjects Seroconverting for LNI Compared to PRNT₅₀ by Dose, Full Analysis Population

		PRNT ₅₀					
Population	Status by LNI	Seroconversion			No Seroconversion		
		N	%	95% CI	N	%	95% CI
Day 29 Post-Dose 1	Seroconversion	x	x.x	x.x, x.x	x	x.x	x.x, x.x
	No Seroconversion	x	x.x	x.x, x.x	x	x.x	x.x, x.x
Day 57 Post-Dose 2	Seroconversion	x	x.x	x.x, x.x	x	x.x	x.x, x.x
	No Seroconversion	x	x.x	x.x, x.x	x	x.x	x.x, x.x

Table 33: Number of Subjects Seroconverting for LNI Compared to PRNT₅₀ by Dose, Per-Protocol Population

		PRNT ₅₀					
Population	Status by LNI	Seroconversion			No Seroconversion		
		N	%	95% CI	N	%	95% CI
Day 29 Post-Dose 1	Seroconversion	X	X.X	X.X, X.X	X	X.X	X.X, X.X
	No Seroconversion	X	X.X	X.X, X.X	X	X.X	X.X, X.X
Day 57 Post-Dose 2	Seroconversion	X	X.X	X.X, X.X	X	X.X	X.X, X.X
	No Seroconversion	X	X.X	X.X, X.X	X	X.X	X.X, X.X

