8. STUDY ASSESSMENTS AND PROCEDURES

8.1 Screening and Immunogenicity Assessments

8.1.1 Screening Procedures

Screening procedures may be done up to 28 days prior to enrollment (Day-28 to Day -1). After informed consent the following assessments are performed to determine eligibility and obtain baseline data:

1. Take a focused medical history, including the following information:
 - History of any chronic medical conditions related to inclusion and exclusion criteria.
 - History of any medication allergies including history of hypersensitivity to any components of the study product.
 - Concomitant medications taken within 60 days prior to signing the ICF will be reviewed with subjects to determine stability of chronic diseases and eligibility.
 - Ask if they are participating in another clinical trial or plan to enroll in another clinical trial during the study period.
2. Women of childbearing potentials should be counseled to either practice abstinence or use at least one primary form of contraception from 30 days prior to receipt of study product until 30 days after receipt of the last dose of study vaccine.
3. Sexually active men should be counseled to use contraception from the date of receipt of the first dose of study vaccine until one month after receipt of the second dose of study vaccine.
4. Women of childbearing potential must have a negative serum HCG pregnancy test at screening and a negative urine HCG pregnancy test prior to each dose of study product.
5. Physical exam (standard exam at screening and targeted exam at enrollment).
6. Height and weight measurement (Calculation of Body Mass Index).
7. Vital signs measurement (including HR, BP, oral temperature).
8. Blood for laboratory evaluations.
 - Serology at screening: HIV, Hepatitis B surface antigen, Hepatitis C antibody.
 - Chemistry at screening: sodium, potassium, bicarbonate, calcium, creatinine, glucose [non-fasting], ALT, AST, and total bilirubin.
 - Hematology at screening: white blood cells (WBCs), hemoglobin, and platelet count.
 - Urine for glucose and protein.

Clinical screening laboratory evaluations will be performed locally by the Duke University Health System Clinical Laboratories. Urine pregnancy tests will be performed by trained research staff. The volume of venous blood to be collected is presented in [Table 3](#).

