8.5 Adverse Events and Serious Adverse Events

8.5.1 Definition of Adverse Events (AE)

Adverse event means any untoward medical occurrence associated with the use of an intervention in humans, whether or not considered intervention-related (21 CFR 312.32 (a)). An AE can therefore be any unfavorable and unintended sign (including an abnormal laboratory finding), symptom, or disease temporally associated with the use of medicinal (investigational) product.

Any medical condition that is present at the time that the subject is screened will be considered as baseline and not reported as an AE. However, if the severity of any pre-existing medical condition increases, it should be recorded as an AE.

Adverse events can be further divided into solicited adverse events and unsolicited adverse events. Solicited adverse events are those for which the study team will specifically query the participant whether they occurred. Unsolicited adverse events are those events that the subject report occurring without being queried about the specific event.

All AEs will be assessed for severity and relationship to study intervention (see Section [8.5.3.2](#)).

All AEs, solicited and unsolicited, will be captured on the appropriate data collection form. Information to be collected for AEs includes event description, date of onset, assessment of severity, relationship to study product and alternate etiology (assessed only by those with the training and authority to make a diagnosis and listed on the FDA Form 1572 as an investigator), date of resolution, seriousness and outcome. AEs occurring during the trial collection and reporting period will be documented appropriately regardless of relationship. In addition, all medically-attended adverse events (MAAEs) (i.e., events for which medical care from a healthcare provider is sought) will be collected through Study Visit 09.

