9.2.1 Safety

The sample size of 10 vaccinated subjects in each dosage group with 5 subjects that receive placebo is small given the early stage (Phase 1) of the product's development, thus the precision of estimate for AEs is limited. Rare adverse events are not demonstrable in a clinical study of this size, however the probabilities of observing one or more AEs given various true event rates and sample sizes are presented in [Table 8](#). If there are adverse events associated with HydroVax-002 YFV in this population, this study will have approximately 80% power to observe at least one such event in a dosage group size of 10 if the true rate is 15%. Comparisons will primarily be made between each vaccine dose group and placebo.

Table 8. Probability of observing one or more adverse events in one dosage group (n=10) given particular true event rates

“True” Unknown Event Rate	Probability of Observing an Event (%)
0.1%	1.0
0.5%	4.9
1.0%	9.6
2.0%	18.3
3.0%	26.3
4.0%	33.5

“True” Unknown Event Rate	Probability of Observing an Event (%)
5.0%	40.1
10.0%	65.1
15.0%	80.3

If there are no observed adverse events among the 10 vaccinated subjects in a dosage group associated with the investigational product, the upper 95% exact confidence bound for the incidence of adverse events will be 30.8%.

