9.4.2 Analysis of Primary Outcome Measures (Safety)

Solicited AEs and laboratory toxicities will be analyzed by taking the most severe response over the follow-up period, dichotomizing into a binary variable (none or mild versus moderate or severe) and using exact confidence intervals to summarize the reactogenicity and toxicity rates. Tabular and graphical summaries of events will be presented for each solicited symptom, by type (local/systemic/toxicity), severity (none or mild, moderate or severe), and time point post-vaccination.

Unsolicited AEs will be coded by the Medical Dictionary for Regulatory Activities (MedDRA) for preferred term and system organ class. The rate and exact 95% confidence intervals of AEs in aggregate, and by MedDRA categories, will be computed. SAEs will be reported by a detailed listing showing the type, MedDRA coding, relevant dates (vaccination and adverse event), severity, relatedness, and outcome for each event. Primary outcome measures include:

- Occurrence of all serious adverse events (SAEs) at any time during the study.
- Occurrence of all Grade 3 unsolicited adverse events (AEs) from first vaccination through day 29 after the second vaccination.
- Occurrence of all Grade 3 laboratory toxicities from first vaccination through day 15 after the second vaccination.
- Occurrence of solicited local AE and reactogenicity signs and symptoms in the 7 days after each vaccination.
- Occurrence of solicited systemic AE and reactogenicity signs and symptoms in the 7 days after each vaccination.
- Occurrence of any AE through day 29 after the second vaccination.

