At least one unsolicited adverse event	x	x	x	x	x	x
At least one related unsolicited adverse event	x	x	x	x	x	x
Mild (Grade 1)	x	x	x	x	x	x
Moderate (Grade 2)	x	x	x	x	x	x
Severe (Grade 3)	x	x	x	x	x	x
At least one severe (Grade 3) unsolicited adverse event	x	x	x	x	x	x
Related	x	x	x	x	x	x
Unrelated	x	x	x	x	x	x
At least one laboratory toxicity	x	x	x	x	x	x
At least one related laboratory toxicity	x	x	x	x	x	x
Mild (Grade 1)	x	x	x	x	x	x
Moderate (Grade 2)	x	x	x	x	x	x
Severe (Grade 3)	x	x	x	x	x	x
At least one severe (Grade 3) laboratory toxicity	x	x	x	x	x	x
Related	x	x	x	x	x	x
Unrelated	x	x	x	x	x	x
At least one serious adverse event ^b	x	x	x	x	x	x
At least one related, serious adverse event	x	x	x	x	x	x
At least one adverse event leading to early termination ^c	x	x	x	x	x	x

N = Number of subjects in the Safety Population and is the denominator for percentages

a: Subjects are counted once for each main category (i.e., non-indented row) regardless of the number of events. Subjects may be counted in more than one main category.

b: A listing of Serious Adverse Events is included in the Serious Adverse Event Listing.

c: As reported on the Adverse Event eCRF.

Table 10: Subject-Level Summary of Solicited Events by Symptom, Severity, Dose, and Treatment Group – Safety Population

Symptom	Severity	Post-Dose 1						Post-Dose 2						Post-Either Dose															
		HydroVax-002 YFV 1 mcg (N = xx)			HydroVax-002 YFV 5 mcg (N = xx)			Placebo (N = xx)			HydroVax-002 YFV 1 mcg (N = xx)			HydroVax-002 YFV 5 mcg (N = xx)			Placebo (N = xx)			HydroVax-002 YFV 1 mcg (N = xx)			HydroVax-002 YFV 5 mcg (N = xx)			Placebo (N = xx)			
		n	%	95% CI	n	%	95% CI	n	%	95% CI	n	%	95% CI	n	%	95% CI	n	%	95% CI	n	%	95% CI	n	%	95% CI	n	%	95% CI	
Any Symptom																													
Any Symptom	None	x	xx	x.x, x.x	x	xx	x.x, x.x	x	xx	x.x, x.x	x	xx	x.x, x.x	x	xx	x.x, x.x	x	xx	x.x, x.x	x	xx	x.x, x.x	x	xx	x.x, x.x	x	xx	x.x, x.x	
	Any Severity																												
	Mild																												
	Moderate																												
	Severe																												
Any Systemic Symptom																													
[Systemic Symptom 1]	None																												
	Any Severity																												
	Mild																												
	Moderate																												
	Severe																												
[Systemic Symptom 2]	None																												
	Any Severity																												
	Mild																												
	Moderate																												

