	Max Severity Post Baseline	HydroVax-002 YFV -1 mcg	XX	X	X.X	X	X.X	X	X.X	X	X.X
		HydroVax-002 YFV -5 mcg	XX	X	X.X	X	X.X	X	X.X	X	X.X
		Placebo	XX	X	X.X	X	X.X	X	X.X	X	X.X

Repeat for all laboratory parameters...

The "Max Post Baseline" rows indicate the maximum severity experienced by each subject at any time point post baseline, including unscheduled assessments.

N = Number of subjects in the Safety population with available laboratory results.

Implementation note: This table will be repeated for all hematology, blood chemistry and urinalysis parameters.

Table 29: Abnormal Laboratory Results Related to Study Treatment by Parameter, Maximum Severity, Study Day, Treatment Group and Parameter – Any Parameter

Parameter	Time Point	Treatment Group	Mild/ Grade 1			Moderate/ Grade 2		Severe/ Grade 3	
			N	n	%	n	%	n	%
[Parameter 1]	Day 4 Post-Dose 1	HydroVax-002 YFV -1 mcg	XX	x	x.x	x	x.x	x	x.x
		HydroVax-002 YFV -5 mcg	XX	x	x.x	x	x.x	x	x.x
		Placebo	XX	x	x.x	x	x.x	x	x.x
	Day 15 Post-Dose 1	HydroVax-002 YFV -1 mcg	XX	x	x.x	x	x.x	x	x.x
		HydroVax-002 YFV -5 mcg	XX	x	x.x	x	x.x	x	x.x
		Placebo	XX	x	x.x	x	x.x	x	x.x
	Day 29 Post-Dose 1	HydroVax-002 YFV -1 mcg	XX	x	x.x	x	x.x	x	x.x
		HydroVax-002 YFV -5 mcg	XX	x	x.x	x	x.x	x	x.x
		Placebo	XX	x	x.x	x	x.x	x	x.x
	Day 4 Post-Dose 2	HydroVax-002 YFV -1 mcg	XX	x	x.x	x	x.x	x	x.x
		HydroVax-002 YFV -5 mcg	XX	x	x.x	x	x.x	x	x.x
		Placebo	XX	x	x.x	x	x.x	x	x.x
	Day 15 Post-Dose 2	HydroVax-002 YFV -1 mcg	XX	x	x.x	x	x.x	x	x.x
		HydroVax-002 YFV -5 mcg	XX	x	x.x	x	x.x	x	x.x
		Placebo	XX	x	x.x	x	x.x	x	x.x
	Max Severity Post Baseline	HydroVax-002 YFV -1 mcg	XX	x	x.x	x	x.x	x	x.x
		HydroVax-002 YFV -5 mcg	XX	x	x.x	x	x.x	x	x.x
		Placebo	XX	x	x.x	x	x.x	x	x.x

Repeat for all laboratory parameters...

The “Max Post Baseline” rows indicate the maximum severity experienced by each subject at any time point post baseline, including unscheduled assessments.

N = Number of subjects in the Safety population with available laboratory results.

Implementation note: This table will be repeated for all hematology, blood chemistry and urinalysis parameters.

Table 30: PRNT₅₀ Geometric Mean Titer (GMT) and Log Neutralizing Titer Index (LNI) Results with 95% Confidence Intervals by Study Day and Treatment Group, Full Analysis Population

Visit	HydroVax-002 YFV 1 mcg			HydroVax-002 YFV 5 mcg			Placebo		
	N	GMT	95% CI	N	GMT	95% CI	N	GMT	95% CI
PRNT₅₀									
Day 1 (pre-vaccination)	XX	X.XX	X.XX, X.XX	XX	X.XX	X.XX, X.XX	XX	X.XX	X.XX, X.XX

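### Laboratory-toxicity counts take the worst post-vaccination grade with no within-subject link to the Day 1 pre-vaccination grade, so abnormalities that pre-date dose 1 and persist are counted as toxicities

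*SAP*

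**What the plan says.** Protocol 9.4.2 states that "laboratory toxicities will be analyzed by taking the most severe response over the follow-up period", and then splits the result into none or mild against moderate or severe. SAP Table 9 has a row for subjects with "At least one laboratory toxicity", with further rows by relatedness and grade. SAP Table 28 tabulates grades by visit and adds a maximum post-baseline line whose footnote says that these "rows indicate the maximum severity experienced by each subject at any time point post baseline, including unscheduled assessments". The laboratory-specific primary endpoint (Protocol 3, SAP 3.2) is every Grade 3 laboratory toxicity from first vaccination to Day 15 after the second.

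Day 1 information exists. Protocol 8.2.2 has safety bloods drawn before the first injection and a Day 1 urine dipstick. Table 28 opens with a Baseline row for each arm, and SAP 6.1 uses the last value at baseline.

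At entry, blood tests may be Grade 1, urine glucose must be negative and urine protein no more than trace (Protocol 5.1). Dipstick blood and leukocyte esterase are graded as safety tests but are not screened (Appendix A, Table 14). On timing, "Screening procedures may be done up to 28 days prior to enrollment".

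For clinical events, Protocol 8.5.1 says: "Any medical condition that is present at the time that the subject is screened will be considered as baseline and not reported as an AE". Footnote 24 of the Schedule of Assessments starts AE collection after the first vaccination.

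**The concern.** A post-vaccination laboratory table should let the reader separate a result that appeared or worsened after the injection from one the subject already had. The planned counts do not. Nothing in SAP 8.4 or the shells defines an emergent toxicity, reports change from Day 1, or cross-classifies Day 1 grade against the later worst grade. The Baseline row of Table 28 is a group total: two of ten graded before dosing and two of ten afterwards could be the same two people or four different ones.

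Pre-existing grades can occur. Grade 1 blood values are admitted, urine blood and leukocyte esterase may be at any grade on Day 1, and blood values can move during the screening interval. No passage expressly makes Day 1 laboratory results a condition for dose 1; Protocol 7.2.1 mentions significant baseline laboratory abnormalities only as an example of a reason for withdrawal.

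At stake is what the safety tables can support in a trial with ten vaccinees per dose and five placebo recipients, where one or two carried-over results visibly move a percentage. The problem is sharper at the Day 57 analysis. SAP 6.3 withholds individual listings then, yet SAP 2.1 expects that analysis to serve a manuscript and the design of later trials.

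**Working it through.** **1. The plan's own figures.** Protocol 9.2.1 claims "approximately 80% power to observe at least one such event in a dosage group size of 10 if the true rate is 15" percent. With n = 10, 1 − (1 − 0.15)^10 = 80.3%, and all nine rows of Protocol Table 8 reproduce. It adds that, with no events, "the upper 95% exact confidence bound for the incidence of adverse events will be 30.8" percent; the two-sided exact bound is 1 − 0.025^(1/10) = 30.8%. Both agree. The documents give no figure for baseline laboratory abnormalities, so everything below rests on assumed rates.

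**2. Which parameters can carry a grade into dose 1.** Sixteen are graded: 12 blood and 4 urine. Urine protein and glucose are excluded at screening from Grade 1 upwards, because Grade 1 starts at 1+. That leaves 14. If each has a 1% to 5% chance of a stable grade, independently (assumption), the share of subjects with at least one is:
- 1 − 0.99^14 = 13.1%
- 1 − 0.95^14 = 51.2%

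Only those that persist or recur after dosing are counted.

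**3. Effect on a group of ten.** Let q be the share of subjects with a pre-existing grade that persists or recurs (assumption). With no vaccine effect, the chance of at least one counted toxicity is 1 − (1 − q)^10. With a true emergent rate p = 5%, the counted rate is 1 − (1 − p)(1 − q).

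**4. Chance imbalance.** Let V ~ Bin(10, q) and P ~ Bin(5, q). The quantity is Pr(V/10 − P/5 ≥ 0.20). For q = 5%:
- P = 0 (0.7738) with V ≥ 2 (0.0861) gives 0.0666
- P = 1 (0.2036) with V ≥ 4 (0.0010) gives 0.0002
- the total is 6.7%, and further terms are negligible

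| q | At least one counted in 10, no vaccine effect | Counted rate if true rate is 5% | Vaccine exceeds placebo by ≥ 20 points, no vaccine effect |
|---|---|---|---|
| 5% | 40.1% | 9.8% | 6.7% |
| 10% | 65.1% | 14.5% | 16.0% |
| 20% | 89.3% | 24.0% | 25.5% |
| 30% | 97.2% | 33.5% | 28.4% |

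**5. What a baseline-conditioned count would show.** Suppose 3 of 10 vaccinees have a graded result after dosing and 2 of them had the same grade on Day 1 (invented counts). As planned, this is 30% (exact 95% CI 6.7 to 65.2). Counting only grades above Day 1, it is 1 of 10, or 10% (0.3 to 44.5).

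**6. Where the effect lands.** A stable Grade 1 blood result enters the any-toxicity row of Table 9 and the Grade 1 column of Table 28. Protocol 9.4.2 pools it with none, so it does not touch the moderate-or-severe rate, nor the Grade 3 endpoint. A Grade 2 or 3 dipstick result for blood or leukocyte esterase, or a blood value that reached that grade between screening and Day 1, can enter both if it persists.

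**The case against.** The strongest reply is that the plan is descriptive, has no formal testing, and treats every arm alike. The counting rule therefore adds noise and does not push the comparison in one direction. That stands, and it limits the point. So does the 9.4.2 dichotomy, which shields the moderate-or-severe rate from stable Grade 1 values. Genuine worsening is not lost either, since a rise from Grade 1 to Grade 2 appears at the higher grade in Table 28.

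It can also be said that Listings 10 to 12 give each subject's abnormal results by study day and that, with 25 subjects, within-subject change can be traced by eye. That is true at the final analysis but not at Day 57. Table 29 and the related rows of Table 9 are not a substitute: they depend on the investigator's causality call, and Protocol 8.5.3.2 allows a temporal relationship to support a rating of related.

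Several stronger readings are tempting and are not supported:
- A reader might infer that the plan ignores Day 1 values altogether. Table 28 has a Baseline row; only the within-subject link is missing.
- A reader might infer that every pre-injection abnormality is counted. One that has resolved by Day 4 and does not recur is not.
- A reader might infer that pre-vaccination clinical conditions are counted as vaccine-period AEs. Conditions present at screening are excluded unless they worsen, history is reviewed again at Visit 01, and collection starts after the first injection. Onset between screening and Day 1 is left unclassified, which is an ambiguity and not shown miscounting.

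Finally, restricting the counts to grades above Day 1 would drop a persistent Grade 3 result and so narrow a protocol-defined primary endpoint. That objection is right, and the fix below respects it.

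**Conclusion.** The point holds in a limited form. The laboratory counts in Protocol 9.4.2 and SAP Tables 9 and 28 cannot distinguish a carried-over grade from a new or worse one, and at Day 57 no other planned output can. The main effect is on the any-toxicity and Grade 1 counts. Grades 2 and 3 are exposed only through the two unscreened urine tests and through changes between screening and Day 1.

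The disturbance is common to all arms, but with ten against five a spurious difference of 20 points or more in favour of placebo arises in about 7% to 28% of trials if 5% to 30% of subjects carry a persisting abnormality. Those shares are assumptions, and the calculation takes subjects as independent with the same rate in both arms. The 13% to 51% in step 2 also assumes independent parameters, which is doubtful for related tests such as AST and ALT, and ignores the Appendix A rule that local normal limits override a conflicting Grade 1 cut-off. No figure stated in the documents changes.

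**What to change.** Keep all planned counts, including every Grade 3 laboratory toxicity. In SAP 8.4 and Tables 9 and 28, add beside them a count of emergent toxicities, defined as a post-vaccination grade above the subject's own Day 1 pre-dose grade. Add a shift table of Day 1 grade by worst post-vaccination grade, by arm and parameter. Produce both at the Day 57 analysis as well as the final one. They are grouped summaries like Table 28, so the decision to defer individual listings is unaffected.

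As a minor clarification, reconcile Protocol 8.5.1 with footnote 24 of the Schedule of Assessments, so that it is clear how a condition starting between screening and Day 1 is classified.

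The cost is one table, one extra row, a definition in the SAP and one clarifying protocol sentence. The Day 1 laboratory results and the Visit 01 history are already collected.

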8.2.2 Safety Clinical Laboratory Tests

Safety labs will be conducted on blood samples obtained on Days 4 and 15 after each vaccination and on the day of, but prior to, administration of the first and second vaccination (day 29 after first vaccination). Safety labs include hematology tests (hemoglobin, WBC, and platelet count) and blood chemistry tests (sodium, potassium, bicarbonate, calcium, creatinine, glucose [non-fasting], ALT, AST, and total bilirubin).

Urine will be tested by dipstick to evaluate glucose, protein, blood, and leukocyte esterase on days 1, 15 and 29 after first vaccination and day 15 after second vaccination.

Safety labs will be tested locally by Duke University Health System Clinical Laboratories.

For laboratory values outside the site's reference ranges, the site PI will document clinical significance in the eCRF. Any result that is deemed clinically significant but does not meet the protocol's grading criteria ([Appendix A](#)) should either be repeated by the study site, or the subject referred for appropriate clinical follow-up.

For any result that meets the protocol's grading criteria (whether or not it is deemed clinically significant), the PI will also assess relationship to study product, action taken with product, and whether the subject was discontinued due to the event. Graded laboratory abnormalities should be followed until either a return to normal or are judged to be stable, as determined by the PI.

In the absence of a diagnosis, any clinical safety laboratory test result that meets the definition of an SAE as determined by the investigator (e.g., life-threatening) must be reported as an SAE using the AE/SAE form set.

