3.2. Endpoints

Primary Outcome Measures:

- Occurrence of all serious adverse events (SAEs) at any time during the study
- Occurrence of all Grade 3 unsolicited adverse events (AEs) from first vaccination through Day 29 after the second vaccination
- Occurrence of all Grade 3 laboratory toxicities from first vaccination through Day 15 after the second vaccination
- Occurrence of solicited local AE and reactogenicity signs and symptoms in the 7 days after each vaccination
- Occurrence of solicited systemic AE and reactogenicity signs and symptoms in the 7 days after each vaccination
- Occurrence of any AE through Day 29 after the second vaccination

Secondary Outcome Measures:

- Percentage of subjects achieving seroconversion ($\geq 1:10$ in plaque reduction neutralizing titer [PRNT₅₀] titer, at Day 29 after first vaccination and at Day 29 after second vaccination
- Geometric mean neutralizing titers at days 15 and 29 after first vaccination and at Days 15, 29, and 57 following second vaccination
- Reverse cumulative distribution curve of neutralizing titers on Days 15 and 29 after first vaccination and at Days 15, 29 and 57 after the second vaccination for each dose group and for all dose groups combined

Exploratory Outcome Measures:

- Geometric mean neutralizing titers at Day 180 following second vaccination
- Reverse cumulative distribution curve of neutralizing titers on Day 180 after the second vaccination for each dose group and for all dose groups combined

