8.4. Clinical Laboratory Evaluations

The following laboratory measurements are collected and will be summarized:

- Hematology tests: White blood cell count, hemoglobin, platelets
- Blood chemistry tests: Sodium, potassium, bicarbonate, calcium, creatinine, glucose (non-fasting), ALT, AST, and total bilirubin.
- Urinalysis

Listings of abnormal laboratory results for hematology ([Listing 10](#)) chemistry ([Listing 11](#)) and urinalysis ([Listing 12](#)) will be provided.

The distribution of laboratory results by severity, study day and treatment group will be presented ([Table 28](#)). Abnormal laboratory results related to study treatment will be provided ([Table 29](#)).

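### The SAP tables that count subjects by worst laboratory grade (Tables 9 and 28) do not apply the endpoint's cut-off at Day 15 after dose 2

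*SAP*

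**What the plan says.** SAP 3.2 lists as a primary outcome "Occurrence of all Grade 3 laboratory toxicities from first vaccination through Day 15 after the second vaccination". Protocol Section 3 and Section 9.4.2 give the same window.

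The analysis text is looser. Protocol 9.4.2 analyses laboratory toxicities by "taking the most severe response over the follow-up period" and does not say there when that period ends. SAP 8.4 introduces Table 28 with "The distribution of laboratory results by severity, study day and treatment group will be presented" and gives no window.

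Two shells count subjects by worst grade:

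- **Table 28**, by parameter, has a maximum post-baseline row. Its footnote defines this as the "maximum severity experienced by each subject at any time point post baseline, including unscheduled assessments".
- **Table 9**, across parameters, has the row "At least one severe (Grade 3) laboratory toxicity", split into related and unrelated. Each subject counts once. No window is stated.

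Table 29 carries the same footnote as Table 28 but covers only results related to study treatment.

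On sampling, Protocol 8.2.2 says "Safety labs will be conducted on blood samples obtained on Days 4 and 15 after each vaccination", with further draws before each dose. The last scheduled draw is therefore Visit 06. In the Schedule of Assessments, safety laboratories at early termination and unscheduled visits are done if indicated, with no visit limit. Protocol 8.2.2 adds: "Graded laboratory abnormalities should be followed until either a return to normal or are judged to be stable".

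**The concern.** An endpoint with a fixed end date should be counted with that end date. Up to Visit 06 every subject is sampled on the same schedule. After it, only subjects with a reason for a test are sampled. A worst-grade count that runs past Visit 06 mixes the two kinds of observation.

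Two things are at stake. The Grade 3 laboratory count in the report may not be the one that SAP 3.2 defines. And a quantity that should be settled by Day 15 after dose 2 could change between the early analysis and the clinical study report without any error in the data.

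**Working it through.** **1. Windows side by side.** Dose 2 is nominally on study Day 29, and the day of vaccination is Day 1.

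| Window | Ends, after dose 2 | Nominal study day |
|---|---|---|
| Primary endpoint (SAP 3.2) | Day 15 | 29 + 14 = 43 |
| Early analysis database (Protocol 9.4.4.2) | about Day 57 | 29 + 56 = 85 |
| Final analysis (last visit) | Day 180 | 29 + 179 = 208 |

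The open-ended row can reach 57 − 15 = 42 days past the endpoint at the early analysis and 180 − 15 = 165 days past it at the final one. These are periods in which a value could arise. They are not periods of continuous sampling.

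**2. Can late values exist?** Yes. Safety laboratories at unscheduled and early termination visits have no visit limit. Other items in the same schedule do: memory aid review is limited to before Visit 06, and several assessments to before Visit 07. The footnote to Protocol Table 3 allows extra draws for adverse event follow-up, and Protocol 8.2.2 follows graded abnormalities until normal or stable.

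**3. Can the endpoint be recovered from other planned output?** Not from the summary tables.

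- The per-visit rows of Table 28 cannot be added up to subjects, because one subject may be abnormal at several visits.
- Where a visit window holds several values, SAP 6.1 keeps the one closest to schedule. An unscheduled Grade 3 value inside the endpoint window may then appear only in the maximum row, where late values are also admitted.
- Listings 10–12 give actual study day, but SAP 6.3 produces no individual listings at the early analysis.

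**4. The plan's own precision figures.** Probability of at least one event with n = 10 and a true rate of 15%: 1 − 0.85^10 = 80.3% (plan: about 80%). Exact two-sided upper 95% limit for 0/10: 1 − 0.025^(1/10) = 30.85% (plan: 30.8%). Both reproduce, and this point does not dispute them.

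**5. Effect of one late Grade 3 value.** Take a subject with no Grade 3 value in the window (in any parameter for Table 9, in that parameter for Table 28). Intervals are exact 95%.

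| Arm | Without it | With it |
|---|---|---|
| Vaccine, n = 10 | 0/10 = 0% (0 to 30.8%) | 1/10 = 10% (0.25 to 44.5%) |
| Placebo, n = 5 | 0/5 = 0% (0 to 52.2%) | 1/5 = 20% (0.5 to 71.6%) |

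The shells for Tables 9, 28 and 29 have no interval column, so readers of those tables would see only the change in count.

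**6. How likely?** The documents give no rate. If the chance q of such a value per subject is assumed to be 1%, 2%, 5% or 10%, the chance of at least one in an arm of 10 is 1 − (1 − q)^10 = 9.6%, 18.3%, 40.1% or 65.1%. The range is illustrative only.

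**The case against.** The strongest reply is that the SAP never names the Table 28 maximum row as the endpoint display. The row is openly labelled as post-baseline, repeats for every parameter, and is consistent with the follow-up-period wording in Protocol 9.4.2. The natural display for the endpoint is Table 9. All of this is correct. But Table 9 has no window either, so the gap remains and is most important there.

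The second reply is that late values can be separated. Table 28 shows each scheduled time point through Day 15 after dose 2, and Listings 10–12 carry actual study day. That holds at the final analysis, by hand. It does not hold at the early analysis, which reports the primary outcomes without listings.

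Third, the analyses are descriptive, there is no formal testing (SAP 6.7), and the early results drive no decision in this trial (SAP 2.1). This stands, and it limits the severity.

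Some stronger readings are tempting and not supported:

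- A reader might infer that every late value comes from a subject who is ill or leaving. Late tests may instead be repeats in a well subject, to follow an abnormality already found or to resolve a technical problem (Protocol 8.2.2 and 8.3). Such a repeat changes the Grade 3 count only if the value first reaches Grade 3 after the window.
- A reader might infer 165 days of symptom-triggered sampling. No draws are scheduled in that period, and at the early analysis it is about 42 days.
- A reader might infer that a Visit 06 draw on Day 16 would be lost. Visit 06 has a window of ±1 day, and no document imposes a literal calendar cut-off, so that loss is hypothetical. It matters only for how the correction is worded.

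**Conclusion.** The mismatch is in the text. The endpoint ends at Day 15 after dose 2, the Table 28 maximum row has no end date, the Table 9 row states no window, and no SAP rule supplies one.

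The size is one subject per late value: 10 percentage points in a vaccine arm, 20 in placebo. This assumes that an indicated test is done after Visit 06, that it is Grade 3, and that the subject had no Grade 3 value in the window. A reader might conclude that the reported rate will differ from the endpoint. The documents show only that it could.

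Table 29 is not an endpoint display, because the endpoint counts all Grade 3 toxicities and that table only related ones. Sample size and precision statements are unaffected. The point is minor, but worth correcting because it concerns a primary endpoint.

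**What to change.** In the laboratory toxicity rows of Table 9 and the maximum row of Table 28, define the endpoint count as first vaccination through the Visit 06 draw (Day 15 ±1 after dose 2), including unscheduled values in that period. Tying the limit to the visit keeps a compliant Day 16 draw in the count.

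Show later values in a separate row for results after Visit 06, so that no safety information is lost. Use the same window in Table 29, for consistency only. One sentence in SAP 8.4 stating that the follow-up period for the laboratory endpoint ends at the Visit 06 draw would also settle the wording of Protocol 9.4.2.

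The cost is footnote wording, one filter and one extra row. No new data are needed. If the change comes after the early unblinded analysis, describe and justify it in the report, as SAP Section 1 requires for deviations from the plan.
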